in Belo Horizonte, a large urban area in the Brazilian state of Minas Gerais, in healthy, hookworm-unexposed adults (n=36) who received up to 100 µg *Na*-GST-1/Alhydrogel[®] with or without 2.5 µg GLA-AF. After no significant adverse events were observed in these volunteers, vaccinations were begun at the hookworm-endemic region of Americaninhas in Minas Gerais; this second part of the trial was a randomized, controlled, double-blind study in which subjects received up to 100 µg *Na*-GST-1/Alhydrogel[®] with or without 2.5 µg GLA-AF (n=60), or the recombinant hepatitis B vaccine (n=6). All volunteers in this study received three intramuscular injections at 0, 2, and 4 months and are being followed for 12 months after the final vaccination. Vaccinations were completed in August 2013 and preliminary immunogenicity results will be available mid 2014. In this study, the *Na*-GST-1/Alhydrogel[®] (with or without GLA-AF) appears to be safe and well tolerated in both hookworm-unexposed and hookworm-exposed adults. No vaccine-related SAEs have occurred and the vaccine appears to be well tolerated, with mild-to-moderate injection site pain and tenderness being the most common vaccine-related adverse events. Also, it is important to note that all volunteers who were screened for study SVI-10-01 were tested for IgE antibodies to *Na*-GST-1: none of these individuals in either Belo Horizonte or Americaninhas had detectable IgE antibodies to the vaccine antigen, as determined by ELISA.

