11 STATISTICAL CONSIDERATIONS

11.1 Study Hypotheses

This study is not designed to statistically test a specific hypothesis. Rather, it is intended to assess the safety, reactogenicity, and immunogenicity of two novel vaccines being co-administered to humans for the first time. The chosen sample size principally facilitates the assessment of safety, as discussed in Section 11.2, *Sample Size Considerations*. Given that, this study will explore, primarily by using descriptive statistics, to assess the following hypotheses:

1. Co-administration of the Na-APR-1 (M74)/Alhydrogel[®] and Na-GST-1/Alhydrogel[®] vaccines will not increase the reactogenicity or safety risk above that of either administered alone.
2. Co-administration of the Na-APR-1 (M74)/Alhydrogel[®] and Na-GST-1/Alhydrogel[®] vaccines will not decrease the functional activity of induced IgG antibodies to either antigen compared to when either is administered alone.
3. Co-administration of the Na-APR-1 (M74)/Alhydrogel[®] and Na-GST-1/Alhydrogel[®] vaccines will not decrease the IgG antibody response to either antigen compared to when either is administered alone.
4. Co-administration of the Na-APR-1 (M74)/Alhydrogel[®] and Na-GST-1/Alhydrogel[®] vaccines will not decrease the avidity of induced IgG antibodies to either antigen compared to when either is administered alone.
5. Co-administration of the Na-APR-1 (M74)/Alhydrogel[®] and Na-GST-1/Alhydrogel[®] vaccines will not decrease the induction of specific MBCs to either antigen compared to when either is administered alone.

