11.3.2 Immunogenicity Review

The proportion of subjects with detectable anti-*Na*-GST-1 and anti-*Na*-APR-1 (M74) responses, and the duration of responses, will be summarized as descriptive measures. Geometric mean antibody responses will be compared between Groups with comparisons made by analysis of variance (ANOVA) tests and pair-wise comparisons by contrasts. Antibody responses will be measured at Days 0, 7, 14, 28, 56, 63, 70, 84, 112, 119, and 126 for interim analysis, with Days 140, 200, 290, and 380 added for final analysis.

To exploit the multiple measures of antibody within each subject, a longitudinal model may be built (if possible) to describe the antibody responses over time. The models will explore if there are any differences between those administered *Na*-APR-1 (M74)/Alhydrogel[®] alone and those co-administered *Na*-GST-1/Alhydrogel[®].

Summary statistics will be used to present exploratory study results of the cellular immune responses to *Na*-GST-1 and *Na*-APR-1 (M74) before and after immunization. To assess the changes in lymphocyte proliferative responses and cytokine/chemokine profiles over time, a generalized estimating equations model with robust standard errors will be constructed. When necessary, data reduction approaches will be used.

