11.4 Final Analysis Plan

The purpose of this trial is to estimate AE rates and patterns of immune response as well as to compare these rates and patterns between the investigational vaccines, when they are administered separately or when they are co-administered.

This section briefly describes the statistical methods to be used; a detailed analytical plan will fully describe the methods. The analytical plan will discuss the planned approaches to missing data. Deviations from the original analytical plan will be thoroughly documented and reported to the Sponsor.

Descriptive and hypothesis-testing approaches will be used to meet the protocol objectives as stated in **Section 3**. Estimates will be presented with their 95% confidence intervals. Formal statistical tests, as outlined below, will be used to compare doses. Statistical tests will use a two-sided significance level of 5%.

Note: For the analyses described below, historical safety data from a Phase 1 clinical trial conducted at the same study site and in the same subject population (study SVI-10-01, see **Section 2.1.6** above for a description of this trial) will be used to obtain a comparison of *Na*-GST-1/Alhydrogel. As well, stored serum and cell specimens from those study participants will be used in the immunological assays to obtain data on subjects administered *Na*-GST-1/Alhydrogel without co-administered *Na*-APR-1 (M74). These specimens from SVI-10-01 will be assayed at the same time as those newly collected from the study described in this protocol.

Primary Objective: To evaluate the safety and reactogenicity of three different dose concentrations of Na-APR-1 (M74) adjuvanted with Alhydrogel® or Alhydrogel® plus GLA-AF and administered either with or without Na-GST-1, in healthy Brazilian adults.

AEs will be coded according to Medical Dictionary of Regulatory Activities (MedDRA™) preferred terms. The frequency, severity, and relationship of AEs per each vaccine formulation and dose cohort of Na-APR-1 (M74) and co-administration status with Na-GST-1 will be presented in tabular form using the MedDRA™ coded term and organized by MedDRA™ System, Organ, and Class (SOC) designations.

- The frequency of immediate, systemic, and local injection site AEs will be summarized by SOC and preferred term.

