2. The IgG level by ImmunoCAP on approximately Day 126.

Analysis Plan:

- a. The proportion of participants with detectable anti-Na-GST-1 and anti-Na-APR-1 (M74) responses will be summarized as a descriptive measure.
- b. IgG levels will be displayed graphically by study group using notched box plots.
- c. Geometric mean antibody responses will be compared between vaccine formulation and dose groups. Comparisons between groups will be made by a one-way analysis of variance (ANOVA) with pair-wise comparisons between groups made by contrasts.
- d. Geometric mean antibody responses for each antigen will be compared using a regression model with main effects for the doses of Na-APR-1 (10, 30 or 100µg), GLA-AF (0 or 5 µg), and Na-GST-1 (0, 100µg).
- e. For antigen-specific log IgG levels, a three-way ANOVA will be conducted, with Na-GST-1, Na-APR (M74) and GLA-AF doses as factors.
- f. Pair-wise comparisons across all combinations of Na-APR-1 (M74) doses, GLA-AF doses (i.e., 0 or 5 µg), and Na-GST-1 co-administration status will be assessed using Tukey's HSD.

Tertiary Objective 1: To assess the impact of co-administration of Na-GST-1 on the duration of the antibody responses to Na-APR-1 (M74), and vice versa.

Tertiary Outcome Measure 1: The IgG antibody response, by an indirect enzyme-linked immunosorbent assay (ELISA) at approximately 7, 14, and 28 days after each vaccination, and approximately 3, 6, and 9 months after the third dose.

Tertiary Outcome Measure 2: The IgG antibody response, by ImmunoCAP at approximately 7, 14, and 28 days after each vaccination, and approximately 3, 6, and 9 months after the third dose.

Analysis Plan:

- a. The proportion of participants with detectable anti-Na-GST-1 and anti-Na-APR-1 (M74) responses will be summarized as a descriptive measure.
- b. Antigen-specific IgG levels will be displayed graphically by study group using notched box plots at each time point.

-
- c. Geometric mean antibody responses will be compared between vaccine formulation and dose groups at each time point. Comparisons between groups will be made by a one-way analysis of variance (ANOVA) with pair-wise comparisons between groups made by contrasts.
 - d. Percent change in IgG antibody levels from days of vaccination to days 7,14 and 28 will be compared between vaccine formulation and dose groups. Values will be reported with 95% confidence intervals.

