 - e. Percent change in IgG antibody levels from vaccination day #1 to #2, and from vaccination day #2 to #3 will be compared between vaccine formulation and dose groups to assess the sustainability of the response from trough to trough. Values will be reported with 95% confidence intervals.
 - f. Percent change in IgG antibody levels from the peak following the third vaccination, to 3, 6 and 9 months after the third vaccination. Values will be reported with 95% confidence intervals.
 - g. Geometric mean antibody responses for each antigen will be compared using a regression model at each time point with main effects for the doses of Na-APR-1 (M74) (10, 30 or 100µg), GLA-AF (0 or 5µg), and Na-GST-1 (0, 100µg)
 - h. For antigen-specific log IgG levels, three-way ANOVAs will be conducted, with Na-APR-1 (M74) dose, GLA-AF dose, and Na-GST-1 co-administration status as factors.
 - i. A longitudinal model will be built to describe the IgG levels over time. Using a longitudinal panel model, differences in antibody isotype levels by dose and formulation of Na-APR-1 (M74) and Na-GST-1 co-administration status will be explored. This will be accomplished using Proc Mixed in SAS 9.3 so the analysis will take account of the correlation between measurements on the same participant.

Tertiary Objective 2: To assess the impact of co-administration of Na-GST-1 on the distribution of IgG subclass responses to Na-APR-1 (M74) and vice versa.

Tertiary Outcome Measure 3: The IgG subclass distribution (IgG1, IgG3, and IgG4) by plate based ImmunoCAP on approximately Day 126.

Tertiary Outcome Measure 4: The IgG subclass distribution by plate based ImmunoCAP each day of vaccination, approximately 28 days later, and approximately 3 and 6 months after the final vaccination.

Analysis Plan:

- a. The proportion of subjects with detectable anti-Na-GST-1 and anti-Na-APR-1 (M74) IgG subclass responses will be summarized at each time point as a descriptive measure.
- b. IgG subclass antibody levels will be displayed graphically by study group using notched box plots at each time point.
- c. Geometric mean antibody responses will be compared between vaccine formulation and dose groups. Comparisons between groups will be made by a one-way analysis

-
- of variance (ANOVA) with pair-wise comparisons between groups made by contrasts.

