- c. A longitudinal model will be built to describe increasing antibody affinity (affinity maturation) over time. Using a longitudinal panel model, differences in affinity maturation by dose and formulation of *Na*-APR-1 (M74) and co-administration with *Na*-GST-1 will be explored. This will be accomplished using Proc Mixed in SAS 9.3, so the analysis will take account of the correlation between measurements on the same participant.

Tertiary Objective 5: To assess the impact of co-administration of *Na*-GST-1 and *Na*-APR-1 (M74) on the production of memory B cells specific for each antigen.

Tertiary Outcome Measure 7: The production of memory B cells specific for each antigen on days of vaccination, approximately 28 days following each vaccination, and 6 and 9 months after the third dose.

Analysis Plan:

- a. The amount of *Na*-GST-1 and *Na*-APR-1 (M74) specific memory B cells will be expressed as a percentage of total lymphocytes present in the blood.
- b. The percentage of specific memory B cells will be displayed graphically by study group at each time point.
- c. Two separate longitudinal panel analyses will test the null hypothesis that average percentages for each of memory B cells are the same in *Na*-APR-1 (M74) groups with and without co-administration of *Na*-GST-1 over time. This will be accomplished using Proc Mixed in SAS 9.3 so the analysis will take account of the correlation between measurements on the same participant.
- d. Mann-Whitney tests will assess the null hypothesis that cytokine levels are the same in the groups at the primary time point of Day 126, two weeks after final vaccination.

Exploratory Objective: To assess the cellular immune responses to the *Na*-GST-1 and *Na*-APR-1 (M74) antigens following immunization.

The following assays will be performed to assess the cellular immune responses to vaccination with *Na*-APR-1 (M74) +/- *Na*-GST-1:

- a. Lymphocyte proliferative responses to *in vitro* stimulation with *Na*-GST-1 or *Na*-APR-1 (M74).
- b. Cytokine and chemokine production *in vitro* in response to stimulation with *Na*-GST-1 or *Na*-APR-1 (M74).
- c. Changes in *in vivo* PBMC subpopulations as determined by flow cytometry.
- d. A longitudinal panel analysis will test the null hypothesis that cytokine and chemokine levels are the same when *Na*-APR-1 (M74) is administered with and without or *Na*-GST-1 and examine for trends over time.

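### The regression prescribed for each antigen has no Na-APR-1-free level, so for anti-Na-GST-1 IgG its Na-GST-1 term measures immunogenicity, not interference from co-administration

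*Protocol*

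**What the plan says.** - **Question asked (Protocol 11.1, hypothesis 3).** Co-administration "will not decrease the IgG antibody response to either antigen compared to when either is administered alone". The secondary objective is likewise the effect of co-administration on antibody to each of the two antigens at Day 126.
- **Model prescribed (11.4, Secondary Objective, item d).** For each antigen, geometric means are compared "using a regression model with main effects for the doses of Na-APR-1 (10, 30 or" 100 µg), GLA-AF (0 or 5 µg) and Na-GST-1 (0 or 100 µg).
- **Repeat (11.4, Tertiary Objective 1, item g).** Responses are "compared using a regression model at each time point with main effects for the doses of Na-APR-1 (M74) (10, 30 or" 100 µg), with the same other terms.
- **Memory B cells (11.4, Tertiary Objective 5, item c).** The null is that "average percentages for each of memory B cells are the same in" Na-APR-1 groups with and without Na-GST-1.
- **Comparator (11.4, Note).** For the analyses that follow it, "stored serum and cell specimens from those study participants will be used in the immunological assays to obtain data on subjects administered" Na-GST-1 without Na-APR-1. The source is study SVI-10-01, described as "conducted at the same study site and in the same subject population".
- **Interim (11.3.2).** On the longitudinal model: "The models will explore if there are any differences between those administered" Na-APR-1 alone and those co-administered Na-GST-1. This section precedes the Note and names no historical comparator.

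**The concern.** Interference with the anti-Na-GST-1 response can be seen only by comparing people given both antigens with people given Na-GST-1 alone. The trial has no such arm: each of the six Groups is split into five subjects on Na-APR-1 plus saline and five on Na-APR-1 plus Na-GST-1. The protocol recognises the gap and plans SVI-10-01 specimens to fill it. Items d and g then fix Na-APR-1 levels that leave those specimens out, and the memory B cell test is confined to Na-APR-1 groups.

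As written, the Na-GST-1 coefficient for anti-Na-GST-1 will be large and almost certainly significant. Under a co-administration objective it could be read as a co-administration result. A loss common to all Na-APR-1 doses would leave no trace. For Na-GST-1-specific memory B cells, the stated null is false whenever the vaccine works.

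The interim report informs the decision on trials in children (2.2.3, 5.3.2, 15.4), and the interim section does not mention the comparator at all.

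**Working it through.** The protocol gives no power or precision figure for this model. Its only calculated figures are the event-detection probabilities in 11.2, which reproduce (for example 1 − 0.9^20 = 87.84%) but do not bear on this point.

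**Inputs from the protocol.** There are 3 Na-APR-1 doses × 2 GLA-AF levels × 2 Na-GST-1 levels with 5 subjects per cell, so n = 60, with 30 given Na-GST-1 and 30 not. Tests are two-sided at 5%.

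**Assumptions.** The rise with Na-GST-1 alone is 1 log10; non-recipients are at 0; SD is 0.3 to 0.5 log10; a 50% loss is log10(2) = 0.301.

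**1. Item d fitted by least squares to the anti-Na-GST-1 cell means**

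| True interference | Na-GST-1 term | Na-APR-1 terms (30, 100 vs 10 µg) |
|---|---|---|
| None | 1.00 | 0, 0 |
| 50% loss at every dose | 0.70 | 0, 0 |
| 50% loss at 100 µg only | 0.90 | 0, −0.151 |

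The Na-GST-1 term equals the response to Na-GST-1 alone plus the mean interference, and the model cannot separate the two. A true response of 4 with no interference and a true response of 5 with interference of −1 give identical fits. This does not depend on the assumed rise or SD. In the third row the loss appears at half size because half the subjects at each dose never received Na-GST-1: 0.301/2 = 0.151.

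**2. Significance of the Na-GST-1 term.** SE = SD × √(1/30 + 1/30) = 0.258 × SD.

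- No loss: z = 1/(0.258 × 0.3) = 12.9, and 7.7 at SD 0.5.
- Uniform 50% loss: z = 0.699/(0.258 × 0.3) = 9.0, and 5.4 at SD 0.5.

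**3. The same model for anti-Na-APR-1.** A true co-administration effect of −0.693 is returned as −0.693. The model works for that antigen.

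**4. Adding a 0 level to item d, with 10 historical subjects.** A uniform loss is recovered (−0.301 at each dose). A loss at 100 µg only is returned as −0.050, −0.050 and −0.201 at 10, 30 and 100 µg, because the non-recipients share the Na-APR-1 terms.

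**5. Na-GST-1 recipients only (30 co-administered plus 10 historical; terms for Na-APR-1 0/10/30/100 and GLA-AF).** The same loss is returned as 0, 0 and −0.301, which is exact.

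**6. Precision of model 5.** With the GLA-AF term, the 0-versus-given contrast averaged over doses rests on the 15 co-administered subjects without GLA-AF against the comparators.

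- SE multiplier = √(1/15 + 1/10) = 0.408, with 40 − 5 = 35 df and t = 2.03.
- 95% interval factor = 10^(2.03 × 0.408 × SD) = 1.77 at SD 0.3 and 2.60 at SD 0.5.
- Power for a 50% loss (noncentral t) is 67% and 30%.
- With 6 to 20 comparators the multiplier runs from 0.483 to 0.342. Across both SDs the interval factor then runs from 1.61 to 3.11.

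The figure of 10 comparators is 60/6. It assumes that the 60 Americaninhas recipients in SVI-10-01 were spread equally over 3 doses and 2 formulations; the protocol does not state the split.

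**7. Comparator population.** Section 2.1.6 says SVI-10-01 began "in Belo Horizonte, a large urban area in the Brazilian state of Minas Gerais, in healthy, hookworm-unexposed adults (n=36"), so 36 of its 102 subjects come from neither the same site nor the same population.

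**The case against.** The Note covers the analyses that follow it, including items d and g, and supplies concurrently assayed Na-GST-1-alone specimens. The bracketed doses could be read as this trial's doses rather than an exhaustive list, with the detail left to the analytical plan. Items c, e and f of the Secondary Objective list no Na-APR-1 levels that exclude a zero, so the contrast could be obtained there. The trial is mainly descriptive and is not powered for group differences. A bare 0 level would also recover a uniform loss, and in the one-dose example its three terms average the true mean loss (0.301/3 = 0.100).

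Part of this stands. The comparator is planned, items c, e and f are open, and a 0 level would cure the uniform-loss case, leaving only the spread across doses distorted. The memory B cell item is a longitudinal test, so it shares the contrast with item d, not the model. The interim wording quoted concerns a longitudinal model that is itself conditional. One may also choose to estimate the effect with GLA-AF included; but 15 of the 30 co-administered subjects receive it, so omitting the term shifts the contrast by half of any GLA-AF effect.

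It does not rescue items d and g. They name their levels and apply them to each antigen. Even with a 0 level, their Na-GST-1 term remains recipient versus never-given. This is a stated model that does not match its objective, not detail deferred to a later plan.

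**Conclusion.** The concern holds and should be fixed. For anti-Na-GST-1, items d and g cannot estimate interference: none of the 60 enrolled subjects supplies Na-GST-1 alone, and the models have no place for the subjects who do. That conclusion needs no assumption about effect size or SD; the 1 log10 rise and the SDs of 0.3 to 0.5 only illustrate how convincing the misdirected term would look. The Na-GST-1 half of the memory B cell test has the same fault, and 11.3.2 names no comparator. The randomised, within-Group anti-Na-APR-1 contrast is valid as written. The precision of the replacement analysis depends on a comparator count and stored visits that the protocol does not give.

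**What to change.** 1. For Na-GST-1-specific outcomes, at interim and final, replace items d and g and the Na-GST-1 half of Tertiary Objective 5 item c with an analysis restricted to Na-GST-1 recipients. These are the 30 co-administered subjects plus the SVI-10-01 Americaninhas recipients of 100 µg Na-GST-1 without GLA-AF, at the matching visit after the third dose. For the longitudinal item, keep the repeated-measures form with this population and coding.
2. Code Na-APR-1 as 0/10/30/100 µg, include GLA-AF (0/5 µg), and drop the Na-GST-1 (0/100) term.
3. For IgG, report the geometric mean ratio of Na-APR-1 given versus not given with its 95% interval. Label it non-randomised and between-study. Level 0 is fully confounded with study, so no separate study term can be fitted.
4. Name the SVI-10-01 comparator in 11.3.2.
5. In the Note, limit the statement about the same site and population to the Americaninhas part of SVI-10-01, and state how many eligible subjects and which stored visits are available.

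The cost is rewording of 11.3.2 and 11.4; no new sampling is proposed, since use of SVI-10-01 specimens is already planned. The price is candour about precision: a small historical subset gives an estimate with a wide interval, not a firm test.

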2.1.8 Studies of Human Immune Responses to *Na*-APR-1 in Endemic Areas

To assess serologic recognition of *Na*-APR-1_{mut} by humans resident in areas of high transmission for *N. americanus*, sera from 648 hookworm-infected individuals from Minas Gerais state, Brazil, were screened for anti-APR-1_{mut} antibody responses. Sixty-two percent showed detectable IgG responses (42% had IgG1, 0.6% IgG2, 15% IgG3, 53% IgG4) and only 0.6% had IgE antibodies to *Na*-APR-1_{mut} (Table 1). There was no association between the presence of antibody and current infection status (positive or negative), intensity of infection (EPG), or age.

Table 1: Anti-*Na*-APR-1_{mut} IgG, IgG subclasses (IgG1-4), IgE, and IgA Antibodies in Brazilian Individuals Living in a Hookworm-Endemic Area.

ELISA method	IgG1	IgG2	IgG3	IgG4	Total IgG	IgE	IgA
Dichotomous, positive [% (n)] ^a	42 (270)	0.6 (4)	15 (97)	53 (343)	62 (401)	0.6 (4)	3 (22)
Quantitative (µg/ml) ^b	0.195 ± 0.104	– ^c	0.123 ± 0.066	0.203 ± 0.136	0.592 ± 0.518	–	–

^a Positivity as indicated by a reactivity threshold, which was determined from a frequency distribution from the upper 95% CI of the frequency distribution from log₁₀ transformed OD values from a panel of sera from Brazilian volunteers not resident in an *N. americanus* transmission area (n=56) and a panel of control sera from U.S. volunteers (24).

^b Values are means ± SD. Amounts were not calculated for samples in which <25 individuals were positive for the antibody.

^c Heterologous interpolation of antibody levels to *Na*-APR-1_{mut} refers to a calibration scheme in which the calibration curve uses reagents that have a different specificity from those used to measure the analyte of interest; in this case, *Na*-APR-1_{mut}-specific antibody ELISA was simultaneously performed alongside a total Ig assay, with the mass values calibrating by interpolating the sample values by the standard curve of the total Ig assay.

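### Prior anti-APR-1 IgG is common in the region, yet the Day 126 models and the detectable-response count ignore Day 0 IgG, and the change analyses use percent change with an unfixed peak

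*Protocol*

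**What the plan says.** **Prior antibody.** Protocol Section 2.1.8 says of sera from 648 hookworm-infected people: "Sixty-two percent showed detectable IgG responses". Table 1 gives 401 positive and a total IgG of 0.592 ± 0.518 µg/ml (mean ± SD). Positive means above a reactivity threshold derived from unexposed sera. Section 2.2.2 says the antigen had not yet been given to anyone in an endemic area, so this IgG reflects natural exposure.

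**Day 126 models (Section 11.4, Secondary Objective).** Item a summarises the proportion with detectable responses. Items c to e compare geometric means by one-way ANOVA, by a regression on the three dose factors, and by a three-way analysis: "For antigen-specific log IgG levels, a three-way ANOVA will be conducted, with" the same three dose factors. None includes Day 0 IgG, although Section 7.2 and Appendix A have it drawn from every subject.

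**Change over time (Section 11.4, Tertiary Objective 1).** Item c is on the geometric scale: "Geometric mean antibody responses will be compared between vaccine formulation and dose groups at each time point". Item g also uses geometric means, item h uses log IgG, and item i is a longitudinal mixed model. Items d to f differ:
- d: "Percent change in IgG antibody levels from days of vaccination to days 7,14 and 28 will be compared between vaccine formulation and dose groups".
- e: "Percent change in IgG antibody levels from vaccination day #1 to #2, and from vaccination day #2 to #3 will be compared" between groups.
- f: "Percent change in IgG antibody levels from the peak following the third vaccination, to 3, 6 and 9 months after the third vaccination".

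For each of d to f: "Values will be reported with 95% confidence intervals". The scale of the interval and the meaning of peak are not given.

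**The concern.** If many subjects enter with measurable and widely varying antibody, three things follow.

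1. A Day 126 comparison without Day 0 IgG leaves explainable variation in the error term and leaves chance baseline differences between arms of 5 uncorrected.
2. A count of detectable responses at Day 126 includes people who were already detectable on Day 0.
3. A percent change divides by a Day 0 value that may be very small, so a few subjects near the assay floor can dominate an arm's mean. Item e has this problem too, because its first trough is Day 0.

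Item f has a separate weakness. A reference chosen because it was the highest of several noisy readings tends to lie above the subject's true level, so the later fall looks larger than it is.

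At stake are the precision and readability of the co-administration comparison at Day 126, and the stated sizes of rise, persistence and waning.

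**Working it through.** **Inputs from the Protocol.** 401 of 648 positive, mean 0.592 and SD 0.518 µg/ml (Section 2.1.8, Table 1); 5 per arm, 10 per Group, 60 in all (Section 4); draws on Days 119, 126 and 140 after dose 3 (Section 7.3).

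**Assumptions, not in the Protocol.** SD of the log10 post/pre ratio 0.3 to 0.5; within-subject noise 0.10 to 0.15 log10; correlation of log Day 0 with log Day 126 IgG 0.3 to 0.7; lognormal levels; a post-dose level of 5 µg/ml in the floor example.

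**1. Baseline share.** 401/648 = 61.9%, which reproduces the stated 62%. The complement is 247/648 = 38.1% (exact 95% CI 34.4% to 42.0%). If this held in the trial, 60 × 0.381 = 22.9 subjects would be below threshold on Day 0. The chance of at least one in an arm of 5 is 1 − 0.619^5 = 91%.

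**2. Baseline spread.** CV = 0.518/0.592 = 0.875. If lognormal, log SD = √ln(1 + 0.875²) = 0.754, or 0.33 log10. This is spread between people, not the SD of a within-person ratio.

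**3. Gain from the covariate.** Residual variance is multiplied by 1 − ρ²:
- ρ = 0.3: 1 − 0.09 = 0.91, a 9% reduction
- ρ = 0.5: 1 − 0.25 = 0.75, a 25% reduction
- ρ = 0.7: 1 − 0.49 = 0.51, a 49% reduction

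The cost is one residual degree of freedom: 60 − 12 = 48 becomes 47 if all 3 × 2 × 2 cells are fitted.

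**4. Floor dependence.** Percent change = 100 × (post/pre − 1). Take 38.1% of subjects at the floor and the rest lognormal with mean 0.592 and log SD 0.754 (reading Table 1's mean as that of positives):
- floor 0.1 µg/ml: mean percent change 2,720%; from the geometric mean 1,878%
- floor 0.05: 4,614%; 2,471%
- floor 0.01: 19,763%; 4,630%

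Moving the floor from 0.1 to 0.01 multiplies the arithmetic mean ratio by 198.63/28.20 = 7.0 and the geometric mean ratio by 47.30/19.78 = 2.4 (which is 10^0.381). The log scale lessens the dependence but does not remove it.

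**5. Coverage if the interval is raw-scale.** A nominal 95% t interval for mean percent change, with lognormal ratios, a 10-fold median rise and 100,000 simulated samples:
- n=5: 88.5% at log10 SD 0.3; 78.3% at 0.5
- n=10: 89.6% and 80.6%
- lower limit below −100% (impossible) at n=5: 19% and 62% of samples

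A t interval on the log ratio covers about 95% throughout. With less spread the shortfall is small: at a natural-log SD of 0.25 the raw interval covers 94.2% at n=5.

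**6. Peak selection.** The expected maximum of three equal-mean normal readings is 0.846 SD above their mean. If the curve is flat over Days 119 to 140 and nothing falls afterwards, the apparent decline is:
- noise 0.10: 1 − 10^(−0.0846) = 17.7%
- noise 0.15: 1 − 10^(−0.1269) = 25.3%

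If the curve clearly peaks at Day 126 (Days 119 and 140 lower by 0.7 and 0.4 on the natural-log scale), a true 50% fall reads as 50% to 52% for natural-log noise up to 0.3, and 57% at 0.5. From a fixed Day 126 value it reads as 50% on the geometric scale.

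**The case against.** The strongest reply is that Section 11.4 calls itself brief and defers the methods to a detailed analytical plan. A percent change can be back-transformed from a log ratio, with nominal coverage, and peak may mean a fixed day. This stands: the interval method, the floor rule and the definition of peak are not errors by their absence, so points 5 and 6 of the working are conditional.

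A reader might infer that 38% of subjects have no Day 0 value, so that their percent change is undefined. The documents do not support that. They are below a reactivity threshold, and Section 8.2.2.1 has levels interpolated from a reference curve. The change would be undefined only if such results were recorded as zero. The survey was also in infected people, although Section 2.1.8 found no association with current infection status. It concerns anti-APR-1 only and bears on Day 0; Days 56 and 112 follow vaccination. No baseline IgG figure is given for Na-GST-1, so no size can be put on that antigen.

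A reader might also infer that Tertiary Objective 1 rests on items d to f. It does not: c, g, h and i analyse the same data, and i addresses duration directly. Item f does not promise a comparison between groups. If noise and curve shape were alike across arms, much of the peak bias would cancel in a comparison.

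Finally, the unadjusted Day 126 contrast for Na-GST-1 is valid, because allocation is randomized within Group, and the trial is not powered for comparison (Section 11.2). That is right. The argument for the covariate is precision, not validity.

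**Conclusion.** The point holds in limited form. Three parts rest on the documents alone. The Day 126 models omit a baseline that every subject provides and that is known to vary widely. Counting detectable responses cannot separate vaccination from prior exposure when 62% of a regional survey were already positive. Items d to f use a measure out of step with the log or geometric scale beside them, and f does not fix its reference day.

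The sizes depend on assumptions. The variance gain is 9%, 25% or 49% at correlations of 0.3, 0.5 or 0.7, and would be nil if Day 0 did not predict Day 126. Coverage of about 78% to 89% at n=5 applies only to a raw-scale interval. The spurious 18% to 25% decline needs a per-subject maximum, a flat curve and noise of 0.10 to 0.15 log10; with a clear Day 126 peak the excess is small. It would go too far to say that the plan's intervals do under-cover or that waning will be overstated.

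The reach is the secondary Day 126 comparison and one tertiary objective. The primary safety objective is untouched.

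**What to change.** In Section 11.4, or in the analytical plan it announces:

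1. Add log Day 0 IgG to the same antigen as a covariate in the Day 126 models.
2. Define response as a stated rise over Day 0 instead of detectability alone.
3. In items d to f, analyse the log ratio and report the geometric mean fold change, or its back-transformed percent, with a 95% interval.
4. State one floor value for results below the assay limit and repeat the analysis with another, because the log scale alone does not remove floor dependence.
5. In item f, use Day 126, already the secondary time point, as the fixed reference.

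This takes a few lines and no new samples, visits or software. The costs are one degree of freedom per model and percent figures replaced by fold changes unless they are back-transformed.
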